A pre-rehabilitation one-to-one assessment will be booked at a time convenient for the patient. The aim of this assessment will be to orientate the patient to the PR intervention and tailor their exercise programme. For this, the ISWT, perceived exertion and breathlessness scale will be used to prescribe the intensity of the exercise component of the PR programme. Patients will be prescribed 65 - 85% of their maximal baseline ISWT performance (can be lower in deconditioned patients) (15).

The adapted PR programme will consist of two main components: exercise and education on the management of COPD. The description, content and frequency of these components will be determined during phase 1 of this project (cultural tailoring).

Control group

Participants randomised to the control group will be offered to attend a 2-3 hour educational session. This will be carried out by the rehabilitations specialists 6-months after study enrolment, once follow-up is complete.

Outcome measures

Data will be collected from patients at the end of the PR programme (6 - 8 weeks) and at sixmonths.

Feasibility study outcomes will include: delivery with fidelity, acceptability to participants, recruitment rate, follow-up rate at 6 months, adherence to intervention, ability to carry out trial procedures, feasibility of methods to measure costs of PR, other COPD-related health care utilisation and patient-incurred costs

Outcome measures to inform a future trial to evaluate clinical and cost effectiveness: HRQoL (SGRQ and EQ-5D-5L); exercise capacity measured by the ISWT; smoking status validated by cotinine; COPD Assessment Test (CAT); self-reported physical activity (IPAQ); self-efficacy; anxiety and depression

(PHQ-9 and GAD-7); self-reported exacerbations; health care utilisation including hospital admissions; and costs/resource use incurred by patients.

Participant timeline

Participants randomised to the intervention group will be invited to a baseline visit/one-to-one prerehabilitation assessment. The number of PR intervention visits per week, and the total length of the PR programme will determined after phase 1 of the project (focus group discussions).

Participants randomised to the control group will be invited to four visits: baseline visit, follow-up visits (end of programme and 6-months) and a 2-3 hour educational and exercise session (6 months).

Sample size

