Data from literature suggests that pilot studies that aim to inform larger trials should include \geq 30 participants to estimate a parameter (16). Based on this, 30 patients will be included in each arm of the trial (total: n=60).

Recruitment

Eligible COPD patients, attending the Chapidze Emergency Cardiology Center, will be invited to take part in the feasibility trial. Those who work in the clinic (e.g. respiratory consultant, or consultant's assistant) will either phone existing clinic patients to provide information about the study, or inform those who are attending their clinic appointment. To encourage recruitment of a range of socioeconomic groups, patients will be recruited from primary care and other hospitals within Tbilisi.

Patients who are interested will be provided with the study invitation documents (including participant information sheet and reply slip) via email or post (through the DHL service, as the national postal service is unreliable). These documents will be provided at the time of the clinic appointment, for those who indicate an interest in-person.

Methods: Data collection, management, and analysis

Data collection methods

Phase 1: Tailoring pulmonary rehabilitation to the Georgian context

Three focus group discussions will be carried out, lasting up to 2 hours each, and will be audio-recorded. Informed consent will be gained at the time of the focus group session. No other research visits will be involved in the phase of the study.

Phase 2: Randomised controlled feasibility trial

Study assessment 1

The baseline research assessment is likely to last approximately 90 - 120 minutes, and include the following components:

Eligibility check: this will be assessed based on the inclusion/exclusion criteria above.
 Spirometry will be carried out by the respiratory team at the Chapidze clinic, who will confirm COPD diagnosis.

- 2. Informed consent: Participants will have the opportunity to ask any questions before completing the consent form with the researcher. As well as consenting to the main study, participants will asked to consent to being contacted and take part in the qualitative interviews linked to this study.
- 3. Completion of the case report form (CRF), which will include the following:
 - a. Documenting patient details (initials, age, sex, ethnicity and employment status)

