 - b. Conducting the Incremental Shuttle Walking Test (ISWT): to be carried out twice; distance walked to be documented in meters; collect various measures pre and post each test (blood pressure, heart rate, oxygen saturations, Borg dyspnoea and RPE scores); record reason for cessation (e.g. breathless, dizziness, painful legs).
 - c. Self-administered participant questionnaire booklet: sociodemographic data (age, sex, ethnicity, education level, marital status, number of dependents; number of adults in the household; and employment); comorbidities; medications; level of dyspnoea (MRC score); smoking status; quality of life and disease specific questionnaires (EQ-5D-5L; St George's Respiratory Questionnaire [SGRQ]; and COPD Assessment Test [CAT]); anxiety and depression (GAD 7 and PHQ-9); self-reported physical activity levels (International Physical Activity Questionnaire [IPAQ]); and health service use (hospitalisations).
 - d. Measuring height and weight to calculate body mass index (BMI)
 - e. Saliva or urine sample to measure cotinine (nicotine levels)
- 4. Randomisation to the treatment or control group

The baseline assessment will be carried out by a member of the research team (exception: the ISWT will be carried out by the trained rehabilitation specialist(s)). The researcher will record all study data on CRFs to ensure standardised data collection/recording. On completion, the researcher will enter the data on to the secure REDcap electronic database.

Study assessment 2

At the end of the PR programme, participants will be invited to a second study assessment. This will include collecting similar data as the baseline assessment:

- 1. Conducting the ISWT (once), and collecting all pre and post-test measures (as detailed above), by the rehabilitation specialist
- 2. Self-administered participant questionnaire including the following: level of dyspnoea (MRC score); smoking status; quality of life and disease specific questionnaires (EQ-5D-5L; St George's Respiratory Questionnaire [SGRQ]; and COPD Assessment Test [CAT]); anxiety and depression (GAD 7 and PHQ-9); self-reported physical activity levels (International Physical Activity Questionnaire [IPAQ]); health service use (hospitalisations); patients costs (for those attending the PR programme); and injuries or health issues as a result of the PR programme.
- 3. Saliva or urine sample to measure cotinine (nicotine levels)

Study assessment 3

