We will report recruitment and follow-up rates, with 95% confidence intervals, as a measure of feasibility of the trial. Although the trial will not be powered to detect a difference between intervention and wait-list control, we will calculate the HRQoL at PR end and 6 months for those allocated to each group; 95% confidence intervals will be provided for estimates obtained. The economic analysis will report questionnaire completion rates, and a cost-consequences analysis. This will include a descriptive analysis of health care costs and EQ-5D-5L scores and an initial estimate of the cost of PR, taking into account the duration of the intervention, format of sessions and number of sessions attended by each participant.

Qualitative data

The Framework approach to data management and analysis will be used for the interviews and focus groups (17).

Methods: Monitoring

Data monitoring

The study will be overseen by a Study Steering Committee, consisting of one representative from each of the following stakeholder groups: patient, clinician/policy maker, research team and, the Breathe Well executive committee. In addition there will be two representatives from the International Scientific Advisory Committee, one of whom will act as chairperson. The Study Steering Committee will meet on a 6-12 monthly basis, as required.

The research team will hold monthly meeting with the Breathe Well executive committee, to discuss current progress and any issues arising.

Harms

The focus group discussions, physiological and questionnaire-based measures pose no risk to the participants.

Non-serious adverse events

The risk of harm associated with study procedures and the intervention are considered to be very low. To further minimise the risk of events, we will:

- 1. Ensure patients meet the eligibility criteria
- 2. Carry out a risk assessment (e.g. of the venue, risks to patients and staff) see appendix 2
- 3. Staff will be trained to manage any risks that are identified in the assessment

Due to the low risk in this study, only the following non-serious adverse events will be collected which will form part of the study outcomes:

- Musculoskeletal injury as a result of the intervention
- Other minor injuries as a result of the intervention
- Non-serious medical events during the rehabilitation that do not require admission to hospital, e.g. participant had to stop due to angina attack that resolved with medication.

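### The only HRQoL analysis named is per group at follow-up; add a baseline-adjusted between-arm difference with its confidence interval

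*Protocol*

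**What the plan says.** **Analysis.** Under Data analysis, Statistical methods, the Protocol first notes that "the trial will not be powered to detect a difference between intervention and wait-list control". It then states that "we will calculate the HRQoL at PR end and 6 months for those allocated to each group; 95% confidence intervals will be provided"; the intervals are attached to estimates in general ("95% confidence intervals will be provided for estimates obtained"). No contrast between the groups is named, and baseline is not mentioned.

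**Purpose.** Under Outcome measures, HRQoL (SGRQ and EQ-5D-5L) comes first in the list headed "Outcome measures to inform a future trial to evaluate clinical and cost effectiveness". The Rationale also asks whether the programme's effects would resemble those seen elsewhere.

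**Data.** The baseline booklet (Study assessment 1, item 3c) includes "quality of life and disease specific questionnaires (EQ-5D-5L; St George's Respiratory Questionnaire [SGRQ]; and COPD Assessment Test [CAT", and the same instruments are repeated at assessments 2 and 3.

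**Size.** "30 patients will be included in each arm of the trial (total: n=60"), allocated 1:1.

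**Order of baseline and randomisation.** The Randomisation section has patients complete all baseline measures after randomisation, and the Participant timeline likewise invites already randomised patients to a baseline visit. Study assessment 1 lists randomisation as item 4, after the case report form and questionnaires in item 3.

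**The concern.** A future trial is designed around a between-arm difference. Two separate follow-up values with their own intervals do not show that difference with its uncertainty. Judging it by whether the two intervals overlap gives the wrong answer.

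With 30 per arm, some chance imbalance in baseline HRQoL is likely, and follow-up values alone leave it uncorrected. The data needed to correct it are already being collected.

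The correlation between baseline and follow-up is needed to size a future trial that adjusts for baseline. It is not among the outputs the protocol names and cannot be worked out from them.

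**Working it through.** **The plan's own figure.** 2 × 30 = 60, which agrees. The protocol rests this on a rule of thumb for pilot studies. It gives no SD, target difference or correlation and no interval width for HRQoL, so there is no precision figure to reproduce.

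**Inputs.** n = 30 per arm and 95% confidence are from the Protocol. The correlation r between baseline and follow-up is assumed and ranged. Results are in units of the within-arm SD at follow-up.

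**Formulas for the 95% half-width.**

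- Mean in one arm: t(n−1)/√n = 2.045/√30 = 0.373 SD.
- Unadjusted difference: t(2n−2) × √(2/n) = 2.002 × 0.258 = 0.517 SD.
- Baseline-adjusted difference: t(2n−3) × √[(2/n)(1−r²)(1 + 1/(2n−4))]. The last factor is the expected small cost of fitting the covariate. At n = 30 this is 0.522 × √(1−r²).

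| r (assumed) | Adjusted half-width (SD) | Ratio to unadjusted 0.517 |
|---|---|---|
| 0 | 0.522 | 1.009 |
| 0.3 | 0.498 | 0.963 |
| 0.5 | 0.452 | 0.874 |
| 0.7 | 0.373 | 0.721 |
| 0.8 | 0.313 | 0.606 |

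Adjustment therefore narrows the interval for the difference by about 13%, 28% or 39% at r = 0.5, 0.7 or 0.8. It gains little at 0.3 and costs about 1% if r is zero. In sample-size terms, n/(1−r²) gives 30/0.75 = 40 per arm at r = 0.5 and 30/0.51 = 59 at r = 0.7.

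**Dropout.** The protocol states no rate. At 24 per arm (assumed), the unadjusted half-width is 0.581 SD and the adjusted ones are 0.509, 0.420 and 0.353 SD at r = 0.5, 0.7 and 0.8. The ratios hardly change: from 27 down to 21 per arm they run from 0.875 to 0.878 at r = 0.5.

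**Reading by overlap.** Two per-arm intervals of equal width just touch when the means differ by 2 × 0.373 = 0.75 SD. The proper interval for the difference already excludes zero beyond 0.517 SD. Overlap therefore sets a bar about 44% too high (0.747/0.517 = 1.44).

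**Chance imbalance.** The baseline difference has standard error √(2/30) = 0.258 SD. The chance that it exceeds 0.25 SD in either direction is about one in three (|z| > 0.97). At r = 0.7, an imbalance of 0.25 SD carries 0.7 × 0.25 = 0.175 SD into the expected follow-up difference.

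**Per-arm mean against adjusted difference.** These are different quantities. The per-arm interval (0.373 SD) is narrower than the adjusted-difference interval until r reaches about 0.70.

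**The case against.** The strongest reply is that the sentence is silent on the point and has not made a wrong choice. It speaks of estimates in general, rules out neither a difference nor baseline adjustment, and is introduced by the statement that the trial is not powered for a comparison. Covariates and models for such outcomes are usually left to a statistical analysis plan, which is not shown here. Describing each arm separately is a defensible choice in a feasibility trial whose first-named measures are recruitment and follow-up rates.

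Much of this stands:

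- A reader might infer that the protocol has chosen unadjusted means in place of an adjusted difference. The text does not say so.
- A reader might also infer that the planned intervals are wider than they need be. They are not: at r = 0.5 the per-arm half-width is 0.373 SD against 0.452 SD for the adjusted difference. The 0.52 SD figure belongs to an unadjusted difference, which the protocol does not name.
- It would be wrong to say that the planned output gives a future trial nothing. If the per-group estimates are means, each SD follows as half-width × √n / t(n−1), and an unadjusted difference with its interval can then be built.
- The sentence concerns HRQoL. ISWT and CAT are listed as separate outcomes, so it cannot be faulted for leaving them out.

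What the reply does not remove is that the one quantity the protocol names does not match its stated use. Lack of power is a reason to avoid a hypothesis test, not a reason to leave out an estimate with its interval. The adjusted difference and the correlation cannot be recovered from per-group summaries, although they remain computable from the trial's dataset.

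**Conclusion.** The point holds as a recommended improvement of modest consequence, not as an error in the protocol. The named HRQoL output should be extended to a baseline-adjusted between-arm difference.

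At 30 per arm, adjusting the difference reduces its 95% half-width from 0.52 SD to about 0.45, 0.37 or 0.31 SD for correlations of 0.5, 0.7 or 0.8. The size rests on those assumed correlations and on a similar SD in both arms; no correlation or SD is given in the protocol.

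The case for the addition does not rest on precision alone: a future trial needs the difference and the correlation whatever r turns out to be. It does depend on a baseline measured before allocation. If patients complete questionnaires when they may already know their arm, their answers may reflect it, which weakens the baseline score as a covariate.

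**What to change.** 1. Reconcile the Randomisation section and Participant timeline with Study assessment 1, so that all baseline measures are completed before randomisation.
2. Keep the per-group summaries and add to Statistical methods:

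> For SGRQ and EQ-5D-5L (and likewise CAT and ISWT) at PR end and 6 months we will estimate the between-arm mean difference, as randomised, by linear regression adjusted for the baseline value, with 95% CI and no hypothesis test. We will also report the SD and the baseline to follow-up correlation.

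For ISWT, state which of the two baseline walks supplies the baseline value.

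The cost is one addition to the analysis text and a correction to the order of procedures. No extra patients, visits or measurements are needed.

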Data on these occurrences will be collected on the participant CRF, and documented on an incident log (appendix 3) during each session. This information will be periodically assessed a member of the research team to identify any further training needs for the rehabilitation specialists.

Patients who are identified to have any suicidal thoughts (according to the PHQ-9 questionnaire at baseline) will be managed according to standard clinical practice in Georgia e.g. referral to a psychologist or primary care doctor.

Serious adverse events

Serious adverse events (SAEs) will be defined as an untoward medical occurrence that results in death, is life-threatening, requires hospitalisation, results in persistent or significant disability or incapacity, or is considered medically significant by the study investigator.

There are some potential SAEs which could be expected to occur during the exercise components of the PR programme, although assessing the eligibility of the participants according to the exclusion criteria will minimise this risk e.g. people with unstable cardiovascular disease, musculoskeletal or neurological conditions the prevent exercise and those with very poor balance.

We do not anticipate SAEs to occur in this study, but this is a group of patients with comorbidities doing an exercise intervention. With suitable monitoring by the rehabilitation specialists, we would expect SAEs to be minimised. But if they do occur, all SAEs will be recorded in the CRF and the database. SAEs will be reported to the chief investigator immediately and within 2 working days of being made aware of the event. If, in the opinion of the local doctor or chief investigator, the event was: 'related' (resulted from the administration of any of the research procedures) and 'unexpected'

(not in our list of expected events), and also occurred within 24h of the study assessment, these will be reported to the lead and local in-country ethics committees, sponsor, UoB team and UoB ethics committee (appendix 4).

Auditing

The study may be subject to inspection and audit by the Chapidze Emergency Cardiology Center, under their remit as sponsor, and other regulatory bodies, to ensure adherence to agreed and relevant principles of GCP and local regulatory frameworks.

Research sites will receive study-specific training before recruitment commences, and all sites will be monitored by the research team throughout the study period.

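### Non-serious adverse events are collected only if attributed to PR or occurring in rehabilitation, so they cannot be compared between arms, and shuttle-walk events are not captured as adverse events

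*Protocol*

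**What the plan says.** Protocol, Harms, Non-serious adverse events, gives a closed list: "only the following non-serious adverse events will be collected which will form part of the study outcomes". It has three entries:

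- The first is "Musculoskeletal injury as a result of the intervention".
- The second covers minor injuries of any other kind, under the same causal condition.
- The third is "Non-serious medical events during the rehabilitation that do not require admission to hospital", with angina that settles on medication as the example.

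These go on the CRF and are "documented on an incident log (appendix 3) during each session". The questionnaire at Study assessment 2 asks about "injuries or health issues as a result of the PR programme". The list for Study assessment 3 has no harm item. The Control group section places the controls' only session "6-months after study enrolment, once follow-up is complete".

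On the risk of the tests, the Harms section opens with "The focus group discussions, physiological and questionnaire-based measures pose no risk to the participants". The subsection that follows rates the risk of study procedures and of the intervention as very low, and gives that low risk as the reason for the short list.

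**The concern.** Whether an event was caused by the intervention is a judgement that should follow collection. Here it is a condition of collection. An injury that the patient or the treating staff do not ascribe to PR is never written down, and in controls no injury can qualify. That has three consequences.

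- The events are declared study outcomes, but one arm of a randomised comparison cannot contribute any.
- The attribution made in the PR arm has nothing to be checked against. The protocol itself describes the participants as patients with comorbidities who are doing exercise, so some injuries and medical events would be expected without PR.
- Both arms repeatedly perform an exercise test, and a non-serious event during that test is neither a result of the intervention nor clearly part of rehabilitation.

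The trial is meant to inform a larger one. The harms collection that the larger trial will need is therefore one of the things to try out here. What is not collected cannot be recovered by any analysis plan.

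**Working it through.** **1. Can a control meet any category?** Set the entries beside the control schedule.

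| Category | Condition | Control during follow-up |
|---|---|---|
| Musculoskeletal injury | caused by the intervention | not possible, no PR received |
| Other minor injury | caused by the intervention | not possible |
| Non-serious medical event | occurs during rehabilitation | not possible |

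The controls' session takes place only when follow-up is complete, so it does not change this. The control count is 0 of 30 by definition.

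**2. Is there another route?** The incident log is kept at rehabilitation sessions. The assessment 2 item carries the same causal condition, and assessment 3 has no harm item. The guidance to the serious adverse event form in Appendix 4 tells staff not to report non-serious events on it. Appendix 2 speaks more generally of recording adverse events in patient files and an incident log, but the Harms section is the text that fixes which events are collected.

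**3. Exposure to the ISWT.** Inputs: 30 per arm (Sample size); two tests at baseline, one at assessment 2, one at assessment 3 (Data collection methods).

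- Total sample: 2 × 30 = 60, as the protocol states.
- Tests per participant: 2 + 1 + 1 = 4.
- Per arm: 4 × 30 = 120. Overall: 4 × 60 = 240.

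This is the planned number without drop-out. A generous reading would treat the PR arm's baseline test as rehabilitation, because it is used to set the exercise prescription. The same test would then be covered in one arm and not in the other, which is no better.

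**4. What the control zero conveys.** An observed 0/30 has an exact two-sided 95% upper limit of 1 − 0.025^(1/30) = 11.6%. That limit holds only if events could have been recorded. Here the zero carries no information.

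**5. What might go unrecorded in controls.** The protocol gives no background rate, so this is an assumption. If a proportion p of controls has an injury or non-serious medical event over 6 months, the expected number is 30p and the chance of at least one is 1 − (1 − p)^30.

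| Assumed p | Expected of 30 controls | Chance of at least one | Recorded under the rule |
|---|---|---|---|
| 5% | 1.5 | 79% | 0 |
| 10% | 3 | 96% | 0 |
| 20% | 6 | 99.9% | 0 |

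**6. What the PR arm still gives.** For illustration, 3 of 30 PR participants with an attributed event would be reported as 10% (exact 95% CI 2.1% to 26.5%). That is a readable description.

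**7. The risk statements.** The first sentence of Harms says the physiological measures carry no risk, while the next subsection says the risk of study procedures is very low. The two do not agree. The definition of a related serious event already covers any research procedure, whereas the non-serious list does not.

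**The case against.** The strongest case is that this is deliberate, targeted collection in a low-risk feasibility trial. No objective or planned analysis compares non-serious events between arms. The stated use of the log is to find training needs for the rehabilitation specialists, and for that a count of PR-attributed and in-session events is enough. Asking about PR injuries when the programme ends, and not again at 6 months, is consistent with that aim.

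Serious harm is also better covered than the short list suggests. All serious adverse events are recorded without restriction by arm or cause, and hospitalisations are asked about in both arms at every assessment. For the ISWT, blood pressure, heart rate, saturation, Borg dyspnoea and exertion scores are taken before and after the test, and the reason for stopping is recorded at baseline. The later assessments refer back to these measures.

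Most of this stands, and it limits the point. Two things remain. The protocol calls these events study outcomes, so their use goes beyond staff training. And a stopping reason is test data: an injury that did not stop the test, or symptoms that came on afterwards, need not appear there, and nothing makes such an event an adverse event.

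**Conclusion.** The concern holds in a limited form. During follow-up controls cannot contribute a non-serious adverse event. Non-serious harms therefore cannot be compared between arms, and attribution to PR has no background rate to be checked against. Non-serious events at the 240 planned ISWTs, 120 of them in controls, are not captured as adverse events. These conclusions rest on the wording of the collection rule and the visit schedule. Only the table of unrecorded control events rests on assumed rates.

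A reader might infer more than the protocol supports:

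- **That the harm outcome cannot be interpreted at all.** It can: the PR-arm count describes PR-attributed events.
- **That background events would swell the PR count against a zero in controls.** The same rule excludes unrelated injuries in the PR arm unless they are misattributed, and no misattribution rate is available, so no excess can be computed.
- **That nothing is known about the safety of the ISWT.** Stopping reasons and pre- and post-test measures are kept, and serious events are covered.
- **That the no-risk sentence is the ground for the short list.** The stated ground is low risk. The sentence needs correcting only because it disagrees with the text that follows it.

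**What to change.** In Harms, Non-serious adverse events:

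- Delete the causal condition from the two injury categories, and collect injuries and non-serious medical events in both arms whether or not they occur in rehabilitation.
- At Study assessments 2 and 3, put the same cause-neutral question to both arms, covering injuries and non-serious medical events since the last visit.
- Use the existing incident log at test visits for any event during or after an ISWT.
- Record relatedness as a separate field, and report counts by arm, all-cause and related.
- Reconcile the opening no-risk sentence with the very low risk stated for study procedures.

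The cost is one question at two visits that already take place, one added field, and use of a form that already exists. The downside is a few more unrelated minor events to record.

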Patients will be invited to attend a final follow-up assessment, after 6 months, to collect the following data:

- 1. The ISWT (once), and collecting all pre and post-test measures (as detailed above, and to carried out by a rehabilitation specialist)
- Self-administered participant questionnaire including the following: level of dyspnoea (MRC score); smoking status; quality of life and disease specific questionnaires (EQ-5D-5L; St George's Respiratory Questionnaire [SGRQ]; and COPD Assessment Test [CAT]); anxiety and depression (GAD 7 and PHQ-9); self-reported physical activity levels (International Physical Activity Questionnaire [IPAQ]); and health service use (hospitalisations)
- 3. Saliva or urine sample to measure cotinine (nicotine levels)

Study assessments 2 and 3 will be carried out by a member of the research team.

Process measures

To be able to assess the feasibility of delivering the PR intervention, the following will be measured:

- 1. Fidelity of delivery of the programme by the rehabilitation specialists: the aim will be to assess whether patients are achieving their prescribed exercise goals which have been set by the rehabilitation specialist. For this, a member of the research team will examine the following patient data over six PR sessions: attendance to all PR sessions (noting number of missed sessions); completion of all prescribed exercises; achieved all sets/repetitions/exercise duration prescribed for each exercise; achieved the recommended exertion score (Borg score); and exercise prescription review (changes by physios based on patient progress). This data will be completed by the patient at each visit, and stored in their research file.
- 2. Participant adherence to the intervention: number of sessions attended; completion of the PR programme; where sessions were carried out (home/clinic) and how many session within each setting; consistent achievement of prescribed goals (e.g. sets/reps/exertion); and education session attendance. This data will be extracted for the patient's research file.
- 3. Ability to carry out trial procedures: baseline data (% complete); follow-up rates (end of programme and 6-months); recruitment rate, and comparison of the characteristics with those who declined to take part; and completeness of data entry.
- 4. Reach: characteristics of the participants; ability to recruit the more socio-economically disadvantaged members of the population; and assessment of geographical reach

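### The rule for managing suicidal thoughts covers only the baseline PHQ-9, although the PHQ-9 is given again at programme end and at 6 months

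*Protocol*

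**What the plan says.** The rule is in the protocol under Harms, Non-serious adverse events: "Patients who are identified to have any suicidal thoughts (according to the PHQ-9 questionnaire at baseline) will be managed according to standard clinical practice". The sentence goes on to give referral to a psychologist or primary care doctor as an example of that practice.

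The PHQ-9 is scheduled three times:

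- **Baseline (Study assessment 1):** it is part of the self-administered questionnaire booklet. "The baseline assessment will be carried out by a member of the research team", apart from the shuttle walk test.
- **End of programme (Study assessment 2):** the questionnaire again includes "anxiety and depression (GAD 7 and PHQ-9); self-reported physical activity levels (International Physical Activity Questionnaire [IPAQ]); health service use (hospitalisations); patients costs". The Outcome measures section gives the timing: "Data will be collected from patients at the end of the PR programme (6 - 8 weeks".
- **6 months (Study assessment 3):** the list again includes "anxiety and depression (GAD 7 and PHQ-9".

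On who runs the later visits, the protocol says: "Study assessments 2 and 3 will be carried out by a member of the research team". The Confidentiality section describes all members of the research team as healthcare professionals.

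**The concern.** By writing this rule, the protocol accepts that any suicidal thought recorded on this instrument calls for a clinical response. The reason for a response is the same at 6 to 8 weeks and at 6 months, and no reason is given for stopping at baseline. Because one time point is named, a reader could take the later PHQ-9 answers to be outcome data only.

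The questionnaire is self-administered, and the protocol does not say who reads the suicidal-thoughts item or when. A first or recurrent disclosure at follow-up could therefore be entered in the database without anything prompting action. This matters most at 6 months, the last scheduled assessment. What is at stake is participant safety; the trial's feasibility results are not affected.

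**Working it through.** The protocol states no figure to reproduce here. The check is a comparison of texts followed by a simple count.

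**Does any other section supply the missing action?**

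| Protocol section | What it covers | Closes the gap? |
|---|---|---|
| Harms, opening statement | Describes questionnaire measures as posing no risk | No |
| Non-serious adverse events, list of events collected | Closed list: injuries from the intervention and medical events during rehabilitation | No; suicidal thoughts are not listed |
| Serious adverse events, and Appendix 4 | Recording and reporting, including events the investigator considers medically significant | No; it requires neither a check of the PHQ-9 nor a referral |
| Ancillary and post-trial care | Says none is necessary, given the low risk | No; it adds no rule |
| Appendix 2, risk assessment | Injury, cardiovascular events, consent, data protection, eligibility, visits, data quality | No; suicidal thoughts are not mentioned |

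**Count of time points**

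- Scheduled PHQ-9 administrations: baseline, programme end, 6 months = 3.
- Named in the rule: 1.
- Outside the rule: 3 − 1 = 2.

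**Count of questionnaires.** The Sample size section plans that "30 patients will be included in each arm of the trial (total: n=60". With complete follow-up the total is 60 × 3 = 180, of which 60 × 2 = 120 lie outside the rule (120/180 = 67%). This is a ceiling, because the follow-up rate is itself an outcome of the trial. Assuming all 60 complete baseline and the same proportion attends each later visit:

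| Assumed follow-up at each visit | Outside the rule | All questionnaires | Share outside |
|---|---|---|---|
| 100% | 2 × 60 = 120 | 60 + 120 = 180 | 67% |
| 70% | 2 × 42 = 84 | 60 + 84 = 144 | 58% |
| 50% | 2 × 30 = 60 | 60 + 60 = 120 | 50% |

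These are counts of questionnaires, not of people with suicidal thoughts, and most of the answers may be negative.

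**The case against.** The strongest reply is that the rule creates no special pathway for participants to lose at follow-up. It says only that they will be "managed according to standard clinical practice in Georgia e.g. referral to a psychologist or primary care doctor", and standard practice does not depend on a sentence in a protocol. The later visits are run by healthcare professionals trained in good clinical practice, and Appendix 2 says most case report forms are completed face to face, so a positive answer may well be seen. A serious case could also be recorded as a medically significant serious adverse event at any time point and would then reach the chief investigator. Working instructions and site training, which are mentioned but not shown, may say who checks the item. On this view the restriction is a drafting slip.

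Much of this stands. No care is shown to be withheld, the practical effect is reduced, and the questionnaire counts say nothing about how many people are affected. The ancillary-care statement should not be read as refusing referral, since it sits alongside the baseline rule.

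The reply does not explain the restriction, however. Research team members also run the baseline visit, and the protocol still judged a written rule necessary there. The serious adverse event route depends on judgement and concerns reporting; it is not a rule to check or refer. If working instructions do cover the follow-up visits, the protocol should agree with them.

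**Conclusion.** The concern holds. A participant-safety rule that the protocol itself states is drawn too narrowly: it covers one of three PHQ-9 administrations and leaves two, in both arms, without a stated clinical action. The count of time points comes directly from the text. The ceiling of 120 of 180 questionnaires rests on 60 participants and full follow-up; the range of 60 to 120 rests on an assumed 50% to 100% attendance at each later visit.

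Participants who are positive at baseline are already under the rule, so the gap mainly concerns new or recurrent thoughts. The point deserves correction because it concerns safety and is easily put right. It does not undermine the design. Confidence is high about the gap in wording; its practical consequence cannot be sized from the protocol.

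**What to change.** In Harms, Non-serious adverse events, replace *at baseline* with *at any study assessment*, and leave management by standard clinical practice as it is.

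Optionally, add that the research team member running each of the three assessments checks the suicidal-thoughts item before the participant leaves. This would also settle who reviews the item at baseline, which the protocol does not say.

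The cost is a one-phrase amendment and, if the optional check is adopted, a brief look at one answer at three visits that already take place. No outcome, sample size or analysis changes.
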